### ***Analysis Methods***

#### **For subjects continued from Studies D1050301 and D1050326**

The number and percentage of subjects with following categories will be summarized by analysis group and analysis subgroup for any extension visit.

- each type of suicidal ideation,
- any suicidal ideation,
- each type of suicidal behavior,
- any suicidal behavior,

- any having self-injurious behavior without suicidal intent,
- any suicidality

In addition, for any extension visit, the number and percentage of subjects with following categories will be also summarized by analysis group and analysis subgroup.

- emergence of suicidal ideation,
- emergence of serious suicidal ideation,
- worsening of suicidal ideation,
- emergence of suicidal behavior,
- emergence of suicidality

Shifts from DB baseline and OL baseline to any post-OL baseline visit (ie, the worst case) in suicidal ideation score will be presented by analysis group and analysis subgroup, to show the percentage of subjects with values 0 ('No ideation present') to 5 ('Active ideation with plan and intent'). For subjects continued from study D1050301, ideation intensity total score will be provided in data listing. Data collected on actual suicide attempts (lethality of actual attempts and potential lethality of attempts) will be presented in a data listing.

## **2.6.12. Udvalg for Kliniske Undersøgelser Side Effect Rating Scale (UKU)**

UKU is only applied to the subjects continued from Studies D1050301 and D1050326.

The UKU consists of 48 adverse effects items, divided into 4 categories: psychic (10 items), neurologic (8 items), autonomic (11 items), and other (19 items). Each item is rated on a 0-3 point scale: 0– no side effects, 1– mild, 2– moderate, 3– severe with causal relationship ('improbable', 'possible', 'probable') also assessed for scores of 1-3. Score of 9 is given if symptom is not assessed or cannot be assessed if it does not apply to a subject (gender, age, sexual maturation); for individual items that are not able to be assessed the rater would line out the item and enter N/A and not assessed would be checked in the symptom checklist.

Specifically, male subjects and female subjects who have not achieved menarche will be rated with a 9 ('Not Assessed) for items 4.7, 4.8, and 4.16, since these items are designed only for female subjects who have achieved menarche; likewise, female subjects will be rated with a 9 ('Not Assessed) for items 4.10, 4.13, and 4.14, since these items are designed for male subjects only.

Unlike other UKU adverse effect item, which is composed of a single assessment, UKU items 4.1 (rash, sub-items: 4.1a~4.1e) and 4.17 (headache, sub-items: 4.17a~4.17c) contains assessments for multiple sub-categories. For these two items, eCRF collects data in the following way: when an adverse event exists, a rating score is to be collected at a specific sub-item level only; when none of these sub-items show adverse event, only item 4.1 (or 4.17) will have value 0 (or 9 when applicable). The rating score related to items 4.1 and 4.17 will be further derived as below:

- If the rating score for at least one of its sub-items is 1 and higher (ie, 1~3), the rating score of item 4.1 (or 4.17) will be set as the most severe value among its sub-items;
- If item 4.1 (or 4.17) has value 0 or 9, its corresponding sub-items will be set as 0 or 9.

In addition to the 48 questions for symptom, two global assessment of effect on functioning are collected in UKU (one by clinician and one by patient); clinical “consequence” with respect to management will be rated by clinician only.

The following four UKU category scores will be calculated as the summation of the assessed individual scores within each category:

- psychic side effects score (range from 0 up to 30),
- neurologic side effects score (range from 0 up to 24),
- and autonomic side effects score (range from 0 up to 33)
- other side effects score (range from 0 up to 48)

Specifically, item with value 9 ('Not Assessed') will not be included in calculation of these category scores. Particularly, UKU other side effects score is gender-specific, ie, items 4.10, 4.13 and 4.14 will not be included in UKU other side effects score calculation for female subjects while items 4.7, 4.8, and 4.16 will not be included in UKU other side effects score calculation for male subjects.

If two or more components are missing (not 'Not Assessed') at a visit, the corresponding UKU category score will be set as missing; when only one component item is missing, the UKU category scores will be calculated based on the available items at a visit. The total UKU score is calculated as the sum of four UKU category scores (ranging from 0 up to 135). If one UKU category score is missing, the total UKU score will be set as missing. Higher values of the total UKU score and four category scores indicate more severe side effects.

Unless otherwise specified, UKU table outputs for following binary effect and the corresponding drug-related effect will be presented by analysis subgroup for analysis timepoint 'any extension visit'.

- Any psychic side effect (ie, Items 1.1 – 1.10)
- Any neurologic side effect (ie, Items 2.1 – 2.8)
- Any autonomic side effect (ie, Items 3.1 – 3.11)
- Any other side effect (ie, Items 4.1 – 4.17)

For UKU assessed in the open-label treatment period, causal relationship to study medication will be grouped into 2 categories (determined by investigators): related (which includes 'possible', 'probable'), and not related ('improbable'). For any UKU assessment prior to the start of the open-label treatment period, causal relationship for UKU items will be 'not related' for previously placebo subjects. During the any open-label treatment, drug-related effect will be defined similarly as above based on the worst case related to the study medication.

A score of 1, 2 or 3 on any UKU item that first occurred or worsened during the open-label treatment period indicated 'cases' of adverse events. Adverse events were conceptualized as a

dichotomous variable, either ‘present’ (1 (mild) or higher) or ‘not present’ (0, 9). The severe order is defined as 3>2>1>0, 9. Both DB baseline and ‘the worst case of DB treatment period’ will be used to derive the ‘Emergence’ and ‘Worsen’ for ‘Any extension visit’ respectively for the parameters below.

- Any Individual side effect (by individual item)
- Any psychic side effect,
- Any neurologic side effect,
- Any autonomic side effect,
- Any other side effect

If one or more of the two required values are missing for ‘emergence of side effect’ or ‘worsen of side effect’, corresponding side effect value will be set as missing.

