subjective restlessness (awareness and related distress), and one global clinical assessment item. All items are anchored and utilize a 4-point scale, except for the global rating which has a 6-point scale (from absence of akathisia through severe akathisia). The subjective and objective items are summed to yield a total score. The BARS can be administered in about 10 minutes. The BARS will be administered by a qualified rater at the site. The same study site rater should perform all BARS assessments for a given subject whenever possible.

Abnormal Involuntary Movement Scale (AIMS): The AIMS is a clinician-rated assessment of abnormal movements consisting of unobtrusive observation of the subject at rest (with shoes removed) and several questions or instructions directed toward the subject. Using a severity scale ranging from 0 (none) to 4 (severe), clinicians rate dyskinesia in several body regions, including the facial area, extremities, and trunk. There are 2 items related to dental status, as well as 3 global impression items assessing overall severity, incapacitation, and the subject's awareness of abnormal movements (Guy, 1976; Munetz, 1988). AIMS raters will be required to meet specific credential and educational criteria before they are certified to rate for this study. The same study site rater should perform all AIMS assessments for a given subject whenever possible.

Udvalg for Kliniske Undersøgelser Side Effect Rating Scale (UKU): The Udvalg for Kliniske Undersøgelser (UKU) Side Effect Rating Scale (Lingjaerde, 1987) is a comprehensive, clinician-rated scale, designed to assess the side effects in patients treated with psychotropic medications. The UKU contains information obtained via interviews with the patient, as well as observations made by the clinician. The UKU consists of 48 questions. A rating can typically be assessed within 30 minutes. Each point on the UKU is assigned a degree of zero, one, two or three. Zero indicates normal; one indicates mild symptoms; two indicates moderate symptoms; and three indicates severe symptoms. The same study site rater should perform all UKU assessments for a given subject whenever possible.

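### SAP 2.6.12 defines the UKU 'other' flag over 17 items, but its own item count and score maxima require 19

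*SAP*

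**What the plan says.** SAP 2.6.12 divides the scale into "psychic (10 items), neurologic (8 items), autonomic (11 items), and other (19 items", and protocol 11.1.2 gives the same overall number: "The UKU consists of 48 questions". Each item is rated 0 to 3. The SAP states maxima of 30, 24, 33 and 48 for the four category scores and 135 for the total.

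The same section defines one yes/no flag per category by item range, each with a drug-related version. The autonomic flag reads "Any autonomic side effect (ie, Items 3.1 – 3.11". The 'other' flag reads "Any other side effect (ie, Items 4.1 – 4.17". Emergence and worsening are then listed for the same named categories without repeating the item ranges. Tables 11.1 and 11.2 compare the open-label period with DB baseline and with the core double-blind period.

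Four further rules bear on the count:
- Some items apply to females only: a rating of not assessed is given to others "for items 4.7, 4.8, and 4.16, since these items are designed only for female subjects who have achieved menarche".
- Some apply to males only: females are rated not assessed "for items 4.10, 4.13, and 4.14, since these items are designed for male subjects only".
- Items 4.1 (five sub-items) and 4.17 (three sub-items) are each reduced to one rating: "the rating score of item 4.1 (or 4.17) will be set as the most severe value among its sub-items".
- The global assessments are extra: "In addition to the 48 questions for symptom, two global assessment of effect on functioning are collected in UKU".

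On the minor point, SAP 2.6.5 gives two HOMA-IR formulas. One has insulin in mU/L with divisor 405 (conventional), the other insulin in μU/L with divisor 22.5 (SI).

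**The concern.** The 'other' category appears to have two definitions in one section: the score is built on 19 items and the flag on 17. A program written from the flag's range could report no 'other' side effect for a subject whose 'other' score is above zero.

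The drug-related flag would miss the same subjects. Emergence, if it uses the printed range, can fail both ways. It misses a new effect on an omitted item. It also counts an effect on a listed item as newly emergent when an omitted item was the only positive one at DB baseline. Worsening behaves similarly when the highest baseline rating sits on an omitted item. The comparison periods come from the core-study SAPs, so a different item set there would add a further inconsistency.

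**Working it through.** **Inputs.** Item counts, the 0 to 3 rating, sex-specific items, flag ranges and maxima are from SAP 2.6.12. The 48 questions are also in protocol 11.1.2. Enrolment numbers are from SAP 1.2.1.

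**1. Reproduce the SAP's figures with 19 'other' items.**
- Items: 10 + 8 + 11 + 19 = 48, as stated.
- 'Other' maximum for a male or a post-menarchal female (three items not applicable): (19 − 3) × 3 = 48, as stated.
- Total maximum: 30 + 24 + 33 + 48 = 135, as stated.
- Working back from 135: (135 − 30 − 24 − 33)/3 + 3 = 19.

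**2. Repeat with the flag's range, 4.1 to 4.17.**
- Items: 10 + 8 + 11 + 17 = 46, not 48.
- 'Other' maximum: (17 − 3) × 3 = 42, not 48.
- Total maximum: 30 + 24 + 33 + 42 = 129, not 135.

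**3. Compare the other flags.** Psychic 1.1–1.10, neurologic 2.1–2.8 and autonomic 3.1–3.11 give 10, 8 and 11 items, each equal to its stated count. Only the 'other' flag departs.

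**4. Look for an innocent source of the gap of two.**
- It is not the two global assessments, which are additional to the 48.
- It is not the sex-specific items. All six (4.7, 4.8, 4.10, 4.13, 4.14, 4.16) lie inside 4.1–4.17.
- Sub-items give the following:

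| Counting of 4.1 and 4.17 | 'Other' items | All items | 'Other' maximum | Total maximum |
|---|---|---|---|---|
| One each, ending at 4.17 | 17 | 46 | 42 | 129 |
| One each, plus two further items | 19 | 48 | 48 | 135 |
| Only 4.17 split | 16 + 3 = 19 | 48 | 48 | 135 |
| Only 4.1 split | 16 + 5 = 21 | 50 | 54 | 141 |
| Both split | 15 + 5 + 3 = 23 | 52 | 60 | 147 |

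Two rows reproduce the SAP's figures: two further items, or 4.17 split while 4.1 is not.

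**5. Reach.** The UKU is given to subjects from D1050301 and D1050326: 271 + 306 = 577 of 702 enrolled (577/702 = 82.2%). The 271 are in the report based on final database lock 1.

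**6. HOMA-IR.** 405/22.5 = 18.0. The SAP's glucose limits in Table 3.1 imply 126/6.993 = 18.018. Glucose conversion alone therefore accounts for the two divisors, and insulin must be in the same unit in both formulas. For illustration, take glucose 90 mg/dL (90/18.018 = 4.995 mmol/L) and insulin 10 mU/L:
- Conventional: 90 × 10/405 = 2.22.
- SI with mU/L: 4.995 × 10/22.5 = 2.22.
- SI with insulin converted to μU/L as printed: 4.995 × 10,000/22.5 = 2220.

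**The case against.** The strongest reply is that the range may be right and the counts wrong. The documents print no item number above 4.17, and splitting 4.17 into three while keeping 4.1 as one reproduces every stated figure. The sub-items also stay in the data, because the SAP assigns them 0 or 9 when the parent item has that value. Against this, the SAP reduces 4.1 and 4.17 to one rating by the same rule, so splitting only one of them conflicts with its own text. This reading does not remove the contradiction; it moves the correction to the counts and maxima. What stands is that the direction of the error is not settled by the documents.

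Two further replies have weight. The range 4.1–4.17 is printed only for the flag and its drug-related version. The scores are sums over each category, and the emergence and worsening lists name the category without a range, so those outputs may already use the full set. Little would be hidden in any case: the SAP also tabulates every individual item, including its emergence and worsening.

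On HOMA-IR, the printed unit is probably a misprint. Nothing in the documents says that insulin will be supplied or entered in μU/L, and the SAP sets no HOMA-IR threshold.

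**Conclusion.** The contradiction is certain on the SAP's own figures: 17 items in the flag, against 19 in the count and in the maxima. Its consequence is conditional. If the category has 19 items, the printed flag covers 14 of the 16 that apply to a male or post-menarchal female, since 17 − 3 = 14 and 19 − 3 = 16. Severity is low: these are secondary descriptive safety outputs in a study without hypotheses, and TEAEs, SAEs and discontinuations due to AEs are unaffected.

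A reader might infer more than the documents support:
- **That items 4.18 and 4.19 are the ones omitted.** This is a guess from the numbering; neither is named anywhere.
- **That 2/16 = 12.5% of 'other' effects are lost, or that 577 subjects are affected.** The first is a share of items under the 19-item reading, not of events. The second is the number enrolled from the two studies using the UKU. The number of changed flags is unknown.
- **That the category and total scores are wrong.** The SAP does not tie the scores to the flag's range. With 19 distinct items they are unaffected; if 4.17's sub-items were summed separately, they would conflict with the one-rating rule.
- **That HOMA-IR will be reported 1000 times too high.** That requires insulin actually to be entered in μU/L.

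**What to change.** 1. Check the 'other' item list against the eCRF and the D1050301 and D1050326 SAPs.
2. If there are 19 items, define the flag and its drug-related, emergence and worsening versions over all of them. Use the same set at DB baseline, in the core double-blind period and in the open-label period.
3. If the category really ends at 4.17, correct the count of 19, the total of 48 and the maxima of 48 and 135, and reconcile any separate counting of sub-items with the one-rating rule.
4. Print one insulin unit (mU/L, equal to μU/mL) in both HOMA-IR formulas and confirm the unit that the laboratory supplies.

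The cost is a few lines of SAP text and code before final database lock 2. SAP section 1 says that the report on subjects with schizophrenia is complete, so the UKU flags and HOMA-IR in the lock 1 outputs need checking. Any correction can go in the full CSR, where SAP 2.1.1 already provides for noting data errors found after lock 1.

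### UKU code 9 counts as 'not present' in the item-level tables, which dilutes the six sex-specific items and leaves unrated applicable items classified as if rated zero

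*SAP*

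**What the plan says.** All of the relevant text is in SAP 2.6.12.

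- Meaning of code 9: "Score of 9 is given if symptom is not assessed or cannot be assessed if it does not apply to a subject". One code therefore carries two states.
- Males and girls before menarche get 9 on "items 4.7, 4.8, and 4.16, since these items are designed only for female subjects who have achieved menarche". Females get 9 on "items 4.10, 4.13, and 4.14, since these items are designed for male subjects only".
- For the binary side-effect endpoints, a rating is a "dichotomous variable, either ‘present’ (1 (mild) or higher) or ‘not present’ (0, 9"). The ranking follows: "The severe order is defined as 3>2>1>0, 9".
- For the category scores, "item with value 9 ('Not Assessed') will not be included in calculation of these category scores".
- The missing-item rule for those scores sets 9 apart from missing: "If two or more components are missing (not 'Not Assessed') at a visit".
- The only exclusion stated for the comparative endpoints begins "If one or more of the two required values are missing for" emergence or worsening, and it makes the result missing. Code 9 is not named there.

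The Analysis Methods part of 2.6.12 plans counts and percentages for each item. Any side effect is shown by analysis subgroup; emergence and worsening are shown by analysis group and subgroup. The groupings in SAP 2.1.9 and 2.1.13 are core study, prior treatment, age and country. Sex is not among them, and no item-specific denominator is given.

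**The concern.** A subject who cannot have a side effect is recorded as not having it, and a subject whose symptom nobody rated is recorded in the same way. For a percentage meant to describe risk, these are different facts, and neither is the same as a rated zero.

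Two consequences follow. First, the six sex-specific items carry a denominator that includes people outside the population at risk. Second, emergence and worsening can be called from a reference value that was never obtained, and absence can be called from an open-label period with no rating.

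Long-term safety is part of the primary objective (SAP 1.1), and the UKU is a safety assessment for two of the three cohorts. The affected items are sex-specific ones, in a paediatric study that also follows prolactin, sex hormones, Tanner stage and menstrual cyclicity. A reader of the item table would naturally take the printed percentage as the risk in those who could be affected.

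**Working it through.** **1. The plan's own figures.** The category sizes are 10, 8, 11 and 19 items, each rated 0 to 3. The stated maxima follow: 10 × 3 = 30, 8 × 3 = 24, 11 × 3 = 33, and for the *other* category (19 − 3) × 3 = 48, because three items are always excluded by sex. The total is 30 + 24 + 33 + 48 = 135. Both 48 and 135 match the SAP. In a sum, dropping an item and scoring it zero give the same result, so the scores are not distorted. In a percentage the two differ, because the subject stays in the denominator.

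**2. The binary rules applied to each pair of values.** The open-label value is the worst case over the period, as in Tables 11.1 and 11.2.

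| Reference | Open-label worst | Emergence | Worsening |
|---|---|---|---|
| 9 | 9 | no | no |
| 9 | 0 | no | no |
| 9 | 1, 2 or 3 | yes | yes |
| 0, 1, 2 or 3 | 9 | no | no |
| missing | any | missing | missing |
| any | missing | missing | missing |

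The first row is every male on items 4.7, 4.8 and 4.16 and every female on 4.10, 4.13 and 4.14: a valid *no* that stays in the denominator. The third row gives emergence with no rated reference. The fourth gives a *no* when the item was never rated in the open-label period.

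**3. Size of the dilution.** Reported rate = true rate among applicable subjects × applicable share. The two UKU cohorts enrolled 271 + 306 = 577 (SAP 1.2.1). The documents give neither the sex mix nor menarche status, so the shares and the 10% rate below are assumptions.

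- Share 30%: 173 applicable, 17.3 with the event, 17.3 / 577 = 3.0%.
- Share 50%: 288 applicable, 28.8 with the event, 28.8 / 577 = 5.0%.
- Share 70%: 404 applicable, 40.4 with the event, 40.4 / 577 = 7.0%.

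Among applicable subjects the figure would be 10% each time. The understatement factor is 1 / share, from 3.3 down to 1.4, and does not depend on the column size.

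**4. Size of the misclassification.** False emergence per item = (share with an applicable item unrated at the reference) × (share of those whose symptom was already there and persisted). Assuming 2% to 10% for the first and 5% to 20% for the second:

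- Low end: 0.02 × 0.05 = 0.1%, or 0.6 of 577 subjects.
- High end: 0.10 × 0.20 = 2.0%, or 11.5 of 577.

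The documents give neither input.

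**The case against.** The strongest reply is that this is an explicit, pre-specified convention with limited reach. The SAP states no denominator for UKU items, so a table shell restricted to applicable subjects would remove the dilution. Counts are printed beside percentages and are not diluted. Gender is tabulated (SAP 2.2.2.1), so a reader could rescale the male-only items roughly by hand. Prolactin and Tanner stage are summarised by gender, and menstrual cyclicity has its own summary. Nothing is tested.

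Much of this stands as a limit on the consequence. It does not remove the point. No restricted shell appears in the documents, and the written rule makes an inapplicable subject a non-missing *no*. The SAP also takes the opposite approach elsewhere: it drops 9 from the category scores, and for D1050325 it withholds the BARS total when a subjective rating is not applicable (2.6.9.1).

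Two stronger readings are tempting and are not supported.

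- A reader might infer that the SAP contradicts its own missing-value rule. It does not, because 2.6.12 separates missing from not assessed. The rule simply does not reach code 9.
- A reader might infer that every change from 9 to present is false emergence. A girl who was pre-menarchal at the reference and later has item 4.7, 4.8 or 4.16 rated 1 to 3 may be a true new onset. The change is false only if the item applied, went unrated, and the symptom was already there. For the same reason, requiring a 0 to 3 rating at both time points would be a poor remedy: it would discard girls who reach menarche during up to 104 weeks of follow-up, and D1050326 enrolled from age 10.

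**Conclusion.** The point holds for the item-level present, emergence and worsening tables. On a literal reading, the six sex-specific items are understated by a factor equal to the inverse of the applicable share: 3.3 to 1.4 for assumed shares of 30% to 70%. The direction is firm under that reading. The size is illustrative, since the sex mix, menarche status and true rates are not in the documents.

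The second effect applies to any item and runs both ways. An applicable item unrated at the reference can create emergence and worsening, and one coded 9 throughout the open-label period can hide an event. Under the assumptions shown, false emergence is 0.1% to 2.0% of subjects per item.

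The UKU category and total scores are not affected. *Any other side effect* is not diluted by sex, because every subject has other applicable items in that category. No test or error rate is involved. This is a correction to descriptive safety tables that is worth making, and it does not threaten the study's conclusions as a whole.

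**What to change.** Amend SAP 2.6.12 for the item-level present, emergence and worsening tables, including the drug-related versions:

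- Split code 9 into *not applicable* and *applicable but not assessed*, using sex and first-menses date. The partial-date rule in SAP 2.1.14.2.4 is worded around Screening, so check menarche during the study against the menstrual calendar that the protocol has reviewed at each visit (11.1.2).
- Report items 4.7, 4.8, 4.16, 4.10, 4.13 and 4.14 only among subjects to whom the item applied during the period, and print that denominator.
- Treat an applicable but unassessed reference value as missing. Do the same for an open-label period with no assessed value.
- Keep *not present* at the reference for a girl who was pre-menarchal then and reached menarche later, so that true new onsets still count.
- Leave the category-score and total-score rules as they are.

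The cost is a few SAP sentences, some reprogramming and smaller denominators that vary by item. The reference values come from the core studies (SAP 2.1.5 and Table 11.2), so code 9 there must be split in the same way. The schizophrenia report from final database lock 1 is already complete (SAP section 1), so the full report needs a footnote wherever these items differ from it. No new data collection should be needed.
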